6.3 DISCONTINUATIONS

The criteria for enrollment must be followed explicitly.

patients will be discontinued from the study in the following circumstances:

- enrollment in any clinical trial involving an IP or enrollment in any other type of medical research judged not to be scientifically or medically compatible with this study
- treating physician decision
 - ✓ Unacceptable toxicity as determined by the participant or site Investigator
 - ✓ The Investigator determines that continuation of treatment is not in the participant's best interests.
 - ✓ Delay of day 1 treatment for >28 days due to treatment-related adverse events. For delays >28 days due to reasons other than treatment-related adverse events, patients may stay on drug if receiving clinical benefit.
 - ✓ if the patient, for any reason, requires treatment with another therapeutic agent that has been demonstrated to be effective for treatment of the patient's gastric or GEJ cancer, discontinuation from the ramucirumab and/or pembrolizumab occurs prior to introduction of the new agent
- patient decision
 - the patient (or the patient's legally acceptable representative) requests to be withdrawn from the study

The reasons for discontinuing treatment will be documented in the participant's medical record.

7. CARE PLAN

7.1 Study Design and Plan

This study is a single arm, open label, single center phase II study of ramucirumab in combination with pembrolizumab in EBV+ or CPS≥5 patients with advanced gastric adenocarcinoma including gastric adenocarcinoma or GEJ adenocarcinoma as a second or third line chemotherapy

[figure not shown]
Patients will receive ramucirumab plus pembrolizumab combination regimen. This study recruits a maximum of 35 patients.

Lilly will only supply ramucirumab and Merck will supply pembrolizumab. Lilly and Merck will not supply other medications used in the care of patients while on this study.

Patients will receive ramucirumab, administered via intravenous (I.V.) infusion over approximately 1 hour, every 2 weeks, at a dose of 8 mg/kg, and pembrolizumab 200 mg will be administered as a 30 minute IV infusion every 3 weeks. (pembrolizumab first followed by

[Type here] [Type here] [Type here]

Pembrolizumab + Ramucirumab(Ver 2.5, Oct 2024)
ramucirumab when concurrently administered on the same day)
- Ramucirumab 8mg/kg on q2W
- Pembrolizumab 200mg on q3W

Assessment of disease control is recommended every 6 weeks (every cycle).

It is recognized that in the course of clinical cancer care, it is not always possible to schedule therapeutic infusions precisely 2 weeks-ramucirumab/3 weeks-pembrolizumab following a prior infusion (because of holidays, travel difficulties, or other circumstances). Accordingly, infusions administered within 3 days before or after the planned time point are acceptable. Administration beyond this window is strongly discouraged.

All patients may continue to receive treatment with the IP, ramucirumab, until there is evidence of progressive disease (PD), unacceptable toxicity, the patient is withdrawn from the study for any other reason, or ramucirumab becomes commercially available and accessible to patients after local marketing authorization. Also, if ramucirumab stops then pembrolizumab be discontinued as well.

Treatment may be discontinued as outlined in Section 6.3

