--	--

[Type here]

[Type here]

[Type here]

Pembrolizumab + Ramucirumab (Ver 2.5, Oct 2024)

	
is detected). Chronic HBV infection with anti-viral agent prophylaxis is allowed.
 
22. Has known liver cirrhosis at a level of Child-Pugh B (or worse) or cirrhosis (any degree) and a history of hepatic encephalopathy or clinically meaningful ascites resulting from cirrhosis. Clinically meaningful ascites is defined as ascites from cirrhosis requiring diuretics or paracentesis.
 
23. The patient is pregnant or breastfeeding

Goal:	To estimate efficacy and safety of combination therapy of Ramucirumab and Pembrolizumab in patients with metastatic gastric or GEJ adenocarcinoma
Planned Sample Size:	
: A maximum of 26 patients (considering 5% drop out rate) will be recruited to this single-arm phase II trial.
 
In this single-arm phase II trial, 25 people were calculated using Simon's two-stage design and a total of 26 patients will be recruited to account for a 5% dropout rate. The sample size is calculated by use of a two-stage minimax Simon's design to control the type I error at 5 % for null hypothesis that, for arm, the true response was 15 % or below and to have 85 % of power if the true response was 40 % or higher. 15 evaluable patients are to be treated in the first stage. If 1 or fewer response are observed in the first stage, the arm will be stopped. If at least 2 responses are observed in the first stage, 10 additional evaluable patients are to be entered onto the second stage. At the final analysis, the null hypothesis will be rejected if at least 7 responses are observed in 25 evaluable patients. RR is reported with its exact 95% CI.

Duration of Study:	Until 100% enrollment from approval regulatory authority
Study design (Dosage & Treatment):	
Patients will continue to receive study treatment, until they demonstrate objective disease progression (determined by modified RECIST 1.1) or until they meet any other discontinuation criteria.
 
 - Ramucirumab 8mg/kg on q2W - Pembrolizumab 200mg on q3W (pembrolizumab first followed by ramucirumab when concurrently administered on the same day)

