12. SAMPLE SIZE

Sample Size Calculation

[Type here]

[Type here]

[Type here]

Pembrolizumab + Ramucirumab(Ver 2.5, Oct 2024)

A maximum of 26 patients will be recruited to this single-arm phase II trial. The primary endpoint of this trial is overall response (OR=PR+CR).

In this single-arm phase II trial, 25 people were calculated using Simon's two-stage design and a total of 26 patients will be recruited to account for a 5% dropout rate.

The sample size is calculated by use of a two-stage minimax Simon's design to control the type I error at 5 % for null hypothesis that, for arm, the true response was 15 % or below and to have 85 % of power if the true response was 40 % or higher. 15 evaluable patients are to be treated in the first stage. If 1 or fewer response are observed in the first stage, the arm will be stopped. If at least 2 responses are observed in the first stage, 10 additional evaluable patients are to be entered onto the second stage. At the final analysis, the null hypothesis will be rejected if at least 7 responses are observed in 25 evaluable patients. RR is reported with its exact 95% CI.

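### Section 7.1 sets a recruitment ceiling of 35 while the synopsis and Section 12 set 26, and no decision rule exists for a sample larger than 25 evaluable patients

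*Combined protocol and SAP*

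**What the plan says.** Three places in the current text give a recruitment maximum.

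- Section 7.1, Study Design and Plan: "This study recruits a maximum of 35 patients".
- Synopsis, Planned Sample Size: "A maximum of 26 patients (considering 5% drop out rate) will be recruited to this single-arm phase II trial".
- Section 12, Sample Size: "A maximum of 26 patients will be recruited to this single-arm phase II trial".

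The figure of 26 is explained in Section 12: Simon's method gives 25, and "a total of 26 patients will be recruited to account for a 5% dropout rate". The design is described as follows: "The sample size is calculated by use of a two-stage minimax Simon's design", chosen "to control the type I error at 5 % for null hypothesis that, for arm, the true response was 15 % or below". The power target is 85% at a response rate of 40%. On the stages, "15 evaluable patients are to be treated in the first stage"; the trial stops with 1 or fewer responses, otherwise 10 more evaluable patients enter, and the null hypothesis is rejected with 7 or more responses in 25.

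Section 13.1.1 divides responders by an ITT population that it defines as all patients given at least one dose of any study treatment.

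**The concern.** All three statements are maxima on recruitment, so they cannot be reconciled as a target and a ceiling, or as screened and enrolled. Nothing explains the 35: no expansion cohort, no replacement allowance and no second calculation is described. It is not 25 inflated at the stated dropout rate.

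Two things are at stake. The first is exposure: a team working to Section 7.1 could enrol 35 − 26 = 9 more patients than the sample-size section justifies. The second is the primary analysis. With more than 25 evaluable patients the plan does not say which of them enter the test, while the ORR denominator grows with every treated patient. In an open-label trial that choice could end up being made after the responses are known. The simplest improvised answer, keeping the cut-off of 7 and counting everyone, would raise the false-positive rate sharply.

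**Working it through.** **Inputs.** Section 12 gives p0 = 0.15, p1 = 0.40, stage 1 n1 = 15 with a stop at 1 or fewer responses, stage 2 of 10, total 25, rejection at r = 7 or more, and dropout of 5%. Section 7.1 gives 35.

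**Step 1: the derivation of 26.** 15 + 10 = 25 evaluable. 25 / 0.95 = 26.3, so 26 is the stated figure to within one patient (strict rounding up gives 27). Applying the same 5% to 35 gives 35 × 0.95 = 33.25, or about 33 evaluable.

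**Step 2: formula.** For a total of n evaluable patients with the stage 1 rule kept,

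P(reject) = Σ over x = 2 to 15 of P(X1 = x) × P(X2 ≥ 7 − x),

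where X1 is binomial(15, p) and X2 is binomial(n − 15, p). The second factor is 1 when x is 7 or more.

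**Step 3: numbers at p = 0.15.** Each cell in the last three columns is P(X1 = x) × P(X2 ≥ 7 − x).

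| x in stage 1 | P(X1 = x) | n = 25 | n = 33 | n = 35 |
|---|---|---|---|---|
| 2 | 0.2856 | 0.0028 | 0.0344 | 0.0486 |
| 3 | 0.2184 | 0.0109 | 0.0611 | 0.0769 |
| 4 | 0.1156 | 0.0208 | 0.0602 | 0.0688 |
| 5 | 0.0449 | 0.0205 | 0.0348 | 0.0370 |
| 6 | 0.0132 | 0.0106 | 0.0125 | 0.0127 |
| 7 or more | 0.0036 | 0.0036 | 0.0036 | 0.0036 |
| **Type I error** | | **0.0692** | **0.2067** | **0.2477** |

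Columns may differ from their totals by 0.0001 through rounding.

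**Step 4: comparison with the plan's own figure.** The written rule at 25 evaluable patients has type I error 6.9% and power 92.6% at p1 = 0.40. The stated 5% is not reproduced even there. That is a separate issue, but it means the right baseline for the effect of extra accrual is 6.9%, not 5%. At 26 counted patients the same cut-off gives 8.3%. The rise attributable to the larger sample is from 6.9% to between 20.7% and 24.8%, a factor of about 3.0 to 3.6.

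**Step 5: what cut-off a larger sample would need (same stage 1 rule).**

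| Evaluable n | 9 or more | 10 or more |
|---|---|---|
| 33 | 4.9% | 1.9% |
| 35 | 6.7% | 2.9% (power 94.1%) |

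The cut-off that holds 5% therefore depends on whether 35 means recruited or evaluable patients. The number in Section 7.1 cannot be adopted without a fresh calculation.

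**The case against.** The strongest reply is that the error rate of the plan is not affected at all. Section 12 ties 7 responses to 25 evaluable patients, and no section applies that cut-off to 35. If the test is read on 25 patients chosen by a rule fixed in advance, later enrolment leaves its error rate unchanged. This stands. A reader might infer that the trial runs at a type I error of about 25%, or that Section 7.1 breaks the primary test; the documents do not support that. The 20.7% to 24.8% describes one foreseeable misuse. What keeps it relevant is that Section 13.1.1 takes every treated patient into the ORR and nothing says which 25 patients form the test set.

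A reader might also set 24.8% against the stated 5%. That overstates the effect, because part of the gap belongs to the boundary at 25.

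Finally, one can argue that 35 is a leftover. It is a single unsupported sentence, while the two passages devoted to sample size agree on 26. Nor is Section 7.1 the section that governs enrolment; that is Section 7.2, which gives no ceiling. This makes 26 the likely intention and lowers the practical risk. It does not remove the contradiction, and only the sponsor can confirm which figure was meant.

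**Conclusion.** The contradiction is real: current text gives recruitment maxima of 35 and 26, and only 26 is derived. Up to 9 patients could be enrolled beyond the justified size, with no decision rule for them. The gap starts at the 26th patient, since the rule stops at 25.

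The effect on the test is conditional. It assumes the cut-off of 7 is carried to the larger sample, the stage 1 stop is kept, and the true response rate is 15%. The lower figure of 20.7% also assumes 5% dropout from 35; the upper figure of 24.8% assumes all 35 are counted. The maximum sample size fixes both patient exposure and the primary analysis, so this should be corrected whether or not that scenario ever arises.

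**What to change.** 1. In Section 7.1, replace 35 with 26 so that it agrees with the synopsis and Section 12.
2. In Section 12, state that the go/no-go test uses the first 25 evaluable patients in enrolment order. This also settles the 26th patient.
3. In Section 13.1.1, state that any further treated patient is included in the ORR estimate and its confidence interval but not in the test. This keeps the existing denominator and separates estimation from the decision.
4. If the sponsor did intend 35, leave Section 7.1 and instead put a recalculated two-stage rule in Section 12 and the synopsis, saying whether 35 is recruited or evaluable.

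Items 1 to 3 cost one number and two sentences, and no patients. Item 4 needs a new calculation and a justification for up to 9 more patients. The mismatch between the 7-response boundary and the stated 5% needs its own correction; aligning the ceiling at 26 does not resolve it.

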	

The diagram illustrates the study timeline. It begins with a 'Screening' phase, followed by 'Cycle 1 (42 days)'. A 'Baseline Fresh Tissue Biopsy' is performed at the start of Cycle 1. Treatment days are marked as D1, D8, D15, D22, D29, and D36. Ramucirumab (R) is administered on D1, D15, and D29. Pembrolizumab (P) is administered on D1 and D22. A legend specifies: R: Ramu : 8mg/kg on D1, D15, D29 (every two weeks); P: Pembro : 200mg on D1, D22 (every three weeks).

 

If ramucirumab had to be stopped due to intolerable toxicity, pembrolizumab will be continued until unacceptable toxicity, disease progression or upto 35 cycles.

Specimen for biomarker and Genetic analysis	
1. Tumor Biopsy Tumor biopsies will be obtained from all subjects in the study. However, tumor biopsy can be exempted in cases considered as not safe or not accessible. It may be performed twice as below if possible.
 
1) Pre-treatment : Obtained at screening (Day 28) from the primary site.2) If disease progresses, optional tumor biopsy may be obtained after it is confirmed. 
2. Blood Collection For analysis of biomarker(ct DNA), peripheral blood of 10 ml will be collected from all patients at every cycle D1 and at confirmed disease progression.

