The treatment schedule remains static regardless of interruptions in ramucirumab administration. Dose delays are only permitted within 3 days after the date of a regularly scheduled treatment. If a patient is unable to receive treatment on or within 3 days before or after the date of his/her regularly scheduled dose for any reason (including AEs), the next dose of ramucirumab should be administered at the first regularly scheduled treatment time point following the resolution of the event causing the delay. (Treatment in this situation [missed dose/cycle] is considered to occur at the subsequently numbered cycle.) Make-up doses occurring between regularly scheduled, every-treatment time points are not recommended.

The patient's physician may discontinue ramucirumab for lack of disease control or toxicity. Patients who experience an AE requiring dose reduction after 2 prior dose reductions should discontinue ramucirumab therapy. In addition, the patient's physician may withdraw a patient from ramucirumab for disease progression, toxicity, or if the treating physician team determines it is in the patient's best interests for any reason. Patients whose performance status worsens by ≥ 2 units should be discontinued from study therapy.

After termination of ramucirumab therapy, the patient will be treated as clinically indicated by the treating physician.

Pembrolizumab

Adverse events (both non-serious and serious) associated with pembrolizumab exposure may represent an immunologic etiology. These adverse events may occur shortly after the first dose or
[Type here] [Type here] [Type here]

Pembrolizumab + Ramucirumab(Ver 2.5, Oct 2024)

several months after the last dose of treatment. Pembrolizumab must be withheld for drug-related toxicities and severe or life-threatening AEs as per Table below. Events of Clinical Interest Guidance Document for supportive care guidelines, including use of corticosteroids.

Dose Modification Guidelines for Drug-Related Adverse Events

Toxicity	Hold Treatment For Grade	Timing for Restarting Treatment	Discontinue Subject
Diarrhea/Colitis	2-3	Toxicity resolves to Grade 0-1.	Toxicity does not resolve within 12 weeks of last dose or inability to reduce corticosteroid to 10 mg or less of prednisone or equivalent per day within 12 weeks.
	4	Permanently discontinue	Permanently discontinue
AST, ALT, or Increased Bilirubin	2	Toxicity resolves to Grade 0-1	Toxicity does not resolve within 12 weeks of last dose.

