	3-4	Permanently discontinue (see exception below) ¹	Permanently discontinue
Type 1 diabetes mellitus (if new onset) or Hyperglycemia	T1DM or 3-4	Hold pembrolizumab for new onset Type 1 diabetes mellitus or Grade 3-4 hyperglycemia associated with evidence of beta cell failure.	Resume pembrolizumab when patients are clinically and metabolically stable.
Hypophysitis	2-3	Toxicity resolves to Grade 0-1	Toxicity does not resolve within 12 weeks of last dose or inability to reduce corticosteroid to 10 mg or less of prednisone or equivalent per day within 12 weeks.
	4	Permanently discontinue	Permanently discontinue
Hyperthyroidism	3	Toxicity resolves to Grade 0-1	Toxicity does not resolve within 12 weeks of last dose or inability to reduce corticosteroid to 10 mg or less of prednisone or equivalent per day within 12 weeks.
	4	Permanently discontinue	Permanently discontinue
Hypothyroidism	2-4	Therapy with pembrolizumab can be continued while treatment for the thyroid disorder is instituted	Therapy with pembrolizumab can be continued while treatment for the thyroid disorder is instituted.
Infusion Reaction	3-4	Permanently discontinue	Permanently discontinue
Pneumonitis	2	Toxicity resolves to Grade 0-1	Toxicity does not resolve within 12 weeks of last dose or inability to reduce corticosteroid to 10 mg or less of prednisone or equivalent per day within 12 weeks.
	3-4	Permanently discontinue	Permanently discontinue
Renal Failure or Nephritis	2	Toxicity resolves to Grade 0-1	Toxicity does not resolve within 12 weeks of last dose or inability to reduce corticosteroid to 10 mg or less of prednisone or equivalent per day within 12 weeks.
	3-4	Permanently discontinue	Permanently discontinue
All Other Drug-Related Toxicity ²	3 or Severe	Toxicity resolves to Grade 0-1	Toxicity does not resolve within 12 weeks of last dose or inability to reduce corticosteroid to 10 mg or less of prednisone or equivalent per day within 12 weeks.
	4	Permanently discontinue	Permanently discontinue

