Note: Permanently discontinue for any severe or Grade 3 drug-related AE that recurs or any life-threatening event. ¹ For patients with liver metastasis who begin treatment with Grade 2 AST or ALT, if AST or ALT increases by greater than or equal to 50% relative to baseline and lasts for at least 1 week then patients should be discontinued. ² Patients with intolerable or persistent Grade 2 drug-related AE may hold study medication at physician discretion. Permanently discontinue study drug for persistent Grade 2 adverse reactions for which treatment with study drug has been held, that do not recover to Grade 0-1 within 12 weeks of the last dose.			

Dosing interruptions are permitted in the case of medical / surgical events or logistical reasons not related to study therapy (e.g., elective surgery, unrelated medical events, patient vacation, and/or holidays). Subjects should be placed back on study therapy within 3 weeks of the scheduled interruption. The reason for interruption should be documented in the patient's study record.

[Type here]

[Type here]

[Type here]

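### The protocol gives opposite instructions on pembrolizumab after a ramucirumab toxicity stop, and incompatible limits on treatment delay

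*Combined protocol and SAP*

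**What the plan says.** **Pembrolizumab after ramucirumab stops.** Three texts apply.

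- Synopsis, Study design: "If ramucirumab had to be stopped due to intolerable toxicity, pembrolizumab will be continued until unacceptable toxicity, disease progression or upto 35 cycles".
- Section 7.1: "Also, if ramucirumab stops then pembrolizumab be discontinued as well". The sentence before it lists unacceptable toxicity among the reasons for ending ramucirumab, and no exception is made for it.
- Section 8.4.1, ramucirumab part: "After termination of ramucirumab therapy, the patient will be treated as clinically indicated by the treating physician". Pembrolizumab is not mentioned.

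**Delay for treatment-related toxicity.** Section 6.3 lists, among the circumstances for discontinuing a patient, "Delay of day 1 treatment for >28 days due to treatment-related adverse events". In the pembrolizumab table of Section 8.4.1, the usual criterion for discontinuing after a hold is "Toxicity does not resolve within 12 weeks of last dose or inability to reduce corticosteroid to 10 mg or less of prednisone" or equivalent within the same 12 weeks.

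**Interruption for other reasons.** Section 6.3: "For delays >28 days due to reasons other than treatment-related adverse events, patients may stay on drug if receiving clinical benefit". Section 8.4.1: "Subjects should be placed back on study therapy within 3 weeks of the scheduled interruption".

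**Cycle length.** The synopsis diagram and Appendix 1 (note b) set a cycle at 42 days. The 35-cycle limit appears only in the synopsis sentence quoted above.

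No section says which text prevails.

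**The concern.** Two clinicians at this single centre, each following the approved protocol, could manage the same patient in opposite ways. One would stop both drugs when ramucirumab proves intolerable; the other would continue pembrolizumab alone. One would take a patient off during a long recovery from toxicity; the other would wait and restart.

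This is first a matter of patient care. It is also a matter of what the results describe. Depending on the rule followed, the time counted in PFS and DOR after a ramucirumab toxicity stop is spent on single-agent pembrolizumab, or on no study drug and possibly on the next line of therapy. Section 13 does not say how those periods will be reported.

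The situation is not remote. The protocol ends ramucirumab specifically for an event needing a further dose reduction after two (Section 8.4.1), Grade 3 or 4 infusion reactions (10.2.6), Grade 3 or 4 arterial events (11.1.2), Grade 3 or 4 bleeding (11.1.3), proteinuria (11.1.4), perforation (11.1.5), RPLS (11.1.6) and liver failure (11.1.9). These rules name ramucirumab only. Section 14.3, by contrast, names both drugs when both are to stop.

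**Working it through.** There is no planned figure to reproduce. The check is to set the texts side by side and put the time limits on one scale.

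**1. Pembrolizumab after ramucirumab stops**

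| Reason ramucirumab ends | Synopsis | Section 7.1 | Section 8.4.1 |
|---|---|---|---|
| Intolerable toxicity | pembrolizumab continues | pembrolizumab stops | physician's judgement |
| Progression | pembrolizumab ends | pembrolizumab stops | physician's judgement |

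The synopsis and Section 7.1 contradict each other only in the first row.

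**2. Treatment-related delay**

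Inputs: pembrolizumab every 21 days (Section 8.1.2); doses on D1 and D22 of a 42-day cycle (synopsis diagram, Appendix 1); 28 days counted from the scheduled day 1 treatment (Section 6.3); 12 weeks counted from the last dose (Section 8.4.1 table).

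Take a patient who received the D22 dose and whose next day 1 dose is delayed by a drug-related toxicity.

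- Section 6.3 limit, in days since the last pembrolizumab dose: 21 + 28 = 49.
- Table limit: 12 × 7 = 84 days, that is 84 − 21 = 63 days past the due date.
- Window of conflict: 84 − 49 = 35 days.

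If the D22 dose was also missed, the last dose was on D1 and the next day 1 falls 42 days later. The Section 6.3 limit is then 42 + 28 = 70 days and the window is 84 − 70 = 14 days. The size depends on which dose came last, but in both cases the 28-day limit is reached before the 12-week one.

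**3. Interruption not caused by treatment**

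Section 8.4.1 expects a return within 3 weeks (21 days). Section 6.3 sets no fixed limit if the patient is benefiting, and explicitly covers delays longer than 28 days.

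**4. The 35-cycle limit**

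With the only cycle length that the protocol defines for the study schedule, 35 × 42 = 1,470 days = 210 weeks, about 4.0 years. The sentence sets this limit only for patients whose ramucirumab was stopped for toxicity. Section 8.4.1 also uses the term treatment cycle loosely for about two weeks, so the intended unit should be stated.

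**5. What the endpoints depend on**

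- ORR, DOR and PFS are defined in the synopsis (Method for Assessment).
- Section 13.1.1 puts every patient with at least one dose of any study treatment in the ORR denominator.
- Sections 7.3 and 10.1.1 continue tumour assessment to RECIST progression after treatment stops.

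A patient moved to one drug, or to none, is therefore still counted and still assessed under the plan.

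**The case against.** **The delay limits could both apply, with the stricter one governing.** They count from different starting points, and the 28-day item sits under the treating physician's decision, so it may not be mandatory. Likewise, the 3-week return could be a target and the clinical-benefit clause an exception to it. This has some force, but no section says so. If the 28-day rule always governed, the 12-week allowance could not be used for a delayed day 1 treatment, because both 49 and 70 days come before 84. If the 28-day rule is discretionary, the text should say that.

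**The statistical damage is limited.** This stands. A reader might infer that the endpoints are undefined, or that the primary conclusion is at risk because one responder separates 6 from 7 at the stated cut-off of at least 7 in 25. The documents do not support that. The definitions, denominator and continued assessment are in place. Only a patient who stops before a response is confirmed could alter ORR, and the documents give neither the rate of ramucirumab toxicity stops nor their timing. Section 7.6 moves patients who start new therapy to telephone survival follow-up, which sits awkwardly with Section 10.1.1, but that is a separate matter.

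**Larger magnitudes are tempting.** Subtracting 28 days from 12 weeks gives 8 weeks, but the two clocks start at different points. Reading 35 cycles as 35 three-weekly doses gives 105 weeks, but no section defines a 21-day cycle, so that is a hypothetical reading and not a measured discrepancy.

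**Conclusion.** The contradictions are real and stand in the current text.

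- For a ramucirumab toxicity stop, the synopsis and Section 7.1 give opposite instructions on pembrolizumab, and Section 8.4.1 adds a third wording.
- For treatment-related delay, Sections 6.3 and 8.4.1 disagree over a 35-day window (day 49 to day 84 after the last pembrolizumab dose). This assumes that the D22 dose was given and the next day 1 dose was delayed.
- For other interruptions, the same two sections differ between no fixed limit with benefit and 3 weeks.

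The number of patients affected cannot be computed, because no stopping rate is given. The consequence is uncertainty about the regimen received. It bears on patient care and on the interpretation of DOR and PFS, and less on ORR; no effect on the ORR decision is demonstrated. The case for correcting the text rests on conflicting treatment instructions, not on a threat to the primary test.

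**What to change.** 1. The sponsor and investigator should reconcile the synopsis, Section 7.1 and Section 8.4.1 on pembrolizumab after a ramucirumab toxicity stop. Which rule is right is a clinical decision that this review does not make.
2. They should likewise reconcile Section 6.3 with Section 8.4.1 on treatment-related delays and on other interruptions, stating for each limit which drug it governs, when the count starts, and whether it is mandatory.
3. State whether the 35 cycles in the synopsis count 42-day cycles (210 weeks) or pembrolizumab doses, and to which patients the limit applies.
4. For patients already treated, list which rule was applied, with the duration of dual and of single-agent treatment.

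No change to the ORR analysis set is needed, since Section 13.1.1 already keeps these patients in. The cost is amendment wording and one listing, with no new procedures.
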